4.4.2 Sleep Diary Data

Sleep diary data are considered as exploratory nature. For both stages, the PD parameters for each period from sleep diary are as below:

- Total sleep time (hours) per night

$$\text{Total sleep time (hrs) per night} = \frac{\text{Sum of daily total sleep time}}{\text{Number of Diary Days}}$$

- Delay (minutes) to sleep onset per night

$$\text{Delay to sleep onset (minutes) per night} = \frac{\text{Sum of daily delay to sleep onset}}{\text{Number of Diary Days}}$$

- Total awake time (hours) per night

$$\text{Total awake time (hours) per night} = \frac{\text{Sum of daily total awake time}}{\text{Number of Diary Days}}$$

- Number of wakes per night

$$\text{Average number of wakes per night} = \frac{\text{Sum of daily number of wakes}}{\text{Number of Diary Days}}$$

- Number of arm or leg thrashing days per week will be calculated as

$$\text{Number of arm or leg thrashing days per Week} = \frac{\text{Sum of days with arm or leg thrashing}}{\text{Number of Diary Days}} \times 7 \text{ days}$$

Arm or leg thrashing is defined as either arm or leg fidget or leg twitching from sleep behavior question.

Based on number of arm or leg thrashing days per week,

- a. Disappearance of arm or leg thrashing from sleep diary – defined as zero days of arm or leg thrashing per week

Except for disappearance of arm or leg thrashing, all the above parameters will be treated as continuous outcomes.

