CP1001 v0.9, Version Date: 27JUL2017

[figure not shown]
31

kept on that fixed dose for a further 2-4 dosing days (3 days if it falls on a Saturday, 4 days if it falls on a Sunday).

The sentinel group will be a group of 10 patients who did not participate in Stage 1. Patients will be given three consecutive doses of the dose which was found to be safe and tolerable in everybody (STDE) and effective in at least some patients in Stage 1 (75 mg in schematic) at home. Patients will self-administer the study medication *daily* for 3 doses (3 days at each dosing level). The dose will be taken upon awakening on an empty stomach along with 8 oz. of water simultaneously to dopamine). The patient will not be allowed to ingest any food for at least 60 minutes after study medication. The daily diary will be completed and results verbally transmitted and emailed to the study coordinator every evening including on week-end days and entered into the electronic data capture system the same night or first thing in the morning. The coordinator will check in with the patients daily, at the end of the day and determine whether there have been any adverse events or CSBM. If the patient has not produced a CSBM within 24 hours of a dose, on at least two of the three days at a given dose, then the patient will be told to proceed to the higher dose of STDE+25mg (eg. 100mg qd) and also to use a suppository followed by an enema if necessary on the evening of the third day (See rescue diagram below). At the end of the second dosing period (100mg for 3 days), the same criteria will be applied to make a determination as to whether to proceed to STDE+50mg (e.g. 125 mg qd) or not. The incremental dosing will continue up to the consistently clinically effective (pro-kinetic) dose, or to the DLT, whichever comes first. Patients who do not have pro-kinetic effect at DLT will be treated with the highest dose at which they did not have a DLT, if it is at least the STDE dose; if the DLT occurred at the STDE dose, then the patient will be terminated. Should a pro-kinetic response not occur at 175 mg, patients will take 175 mg for the 2-4 additional fixed-dose dosing days and 6 randomized dosing days (assuming randomization is to treatment). DLT will be the dose inducing repeated vomiting or diarrhea within 24 hours of dosing. The lowest dose producing a CSBM on 2/3 consecutive doses will be noted as the pro-kinetic dose (LSTDEi i.e. consistently clinically effective safe and tolerable dose for that particular individual). Patients will be kept on the lowest dose producing a pro-kinetic effect for another 2-4 days prior to randomization in Period 4. The Enterin CMO will review the stool diaries prior to randomization to ensure dosing adequacy. PAC-QOL and PAC-SYM will be repeated prior to randomization at Visit 3. CSBM during the fixed dose period will

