4.2 Selection Criteria

Patients will be selected by individual site PIs from among PD patients seen at the tertiary referral center. Patients will be screened for the presence of non-motor symptoms of PD, specifically constipation and REM behavior disorder (RBD). *The population will be enriched with respect to NMS, specifically sleep delay and sleep fragmentation problems, and RBD.* The presence of constipation at baseline will be established according to the Rome IV criteria and other inclusion criteria below. Onset of constipation before or after a diagnosis of PD will specifically be noted and its duration and severity established. The daily stool diary will be analyzed at the end of the two week run-in period to establish the presence of severe constipation on rescue medication alone (does not apply to Stage 1). Patients with two or fewer complete, spontaneous bowel movements per week will be entered into the treatment phase. RBD will be determined by history and questionnaire. The use of anti-depressants, anti-cholinergics and anti-psychotics will be permitted as long as patients are on a stable dose of medication.

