2 STUDY DESIGN OVERVIEW

2.1 Overall Study Design

This is a single-dose, multiple-dose, randomized, double-blinded, placebo-controlled, two-staged study in Parkinson's disease subjects with constipation. The study will consist of two stages, each with run-in period and dosing periods and followed by a wash-out period of 2 weeks. Stage 1 will consist of 10 subjects while Stage 2 will consist of 40 subjects to ensure at least 34 evaluable subjects are obtained. During Stage 1, after providing informed consent, subjects will be screened for eligibility. Qualified subjects will proceed through all the dose escalations of ENT-01 starting at 25 mg and ending at 200 mg or at the dose at which s/he experiences a dose limiting toxicity (DLT). Stage 1 is staggered, where the first two subjects will be administered a single dose of 25 mg first. The rest of the subjects will be dosed after the first two subjects have been observed for 72 hours with no safety concerns. The doses to be tested are 25mg, 50mg, 75mg, 100mg, 125mg, 150mg, 175mg and 200mg. Subjects will then be observed off study drug for two weeks during the wash-out period. STDE (Safe and Tolerable dose in all and pro-kinetic Effect in at least some) dose will be identified and carried over to Stage 2.

In Stage 2 under protocol dated 27 July 2017, subjects who signed the informed consent and are eligible will go through a multiple dose escalation (3 dosing days at each dose) period. The dose range is 75 mg up to 175 mg with an increment of 25 mg for next higher dose. Ten subjects will be in the sentinel group and will be dosed first. The dose at which the subject experiences a consistent pro-kinetic effect (spontaneous, complete stool in at least 2/3 consecutive doses) without a DLT will be the dose selected going forward for that subject. This will be the LSTDEi (i.e. consistently clinically effective safe and tolerable dose for that particular individual). After the LSTDEi is established, subjects will continue to take this dose for 2-4 days, followed by randomization on the LSTDEi dose with a 1:1 ratio to ENT-01 or placebo in block sizes of 4 for a 6-day period (period 4). Seven subjects from the ENT-01 group and three subjects from the control group will be in the PK group and have the PK measurement taken. The rest will be in the non-PK group. All the subjects will then enter the wash-out period for two weeks.

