4.4 Pharmacodynamic Evaluations

Unless otherwise stated, the following pharmacodynamic (PD) variables are evaluated for both Stage 1 and Stage 2. All PD parameters will be defined for each period. The periods under consideration for summary and analyses are run-in (i.e., baseline), each dosing period or treatment period (as applicable), and washout period (i.e., follow-up period).

For Stage 1 stool diaries, the baseline PD parameters will be calculated using all diaries from run-in period; dosing period PD parameters will be calculated on dosing day immediately following each dose (for CSBM and SBM after dose, need to consider the day before dosing for the rescue medications use); and washout PD parameters will be calculated using diaries excluding the first day diaries (i.e., this one day diaries will be attributed to last dosing period).

For Stage 2 stool diaries, all the diaries for each dosing period will be used for the calculation of PD parameters. The washout period started 24 hours of last dose.

For Stage 1 sleep diaries, PD parameters will be calculated using all diaries from run-in period; up to last dosing period. The first 7-day diaries after last dosing period will be attributed to last dosing period and the second 7-day diaries after last dosing period will be attributed to washout period.

For Stage 2 sleep diaries, PD parameters will be calculated using all diaries from run-in period; all diaries in each dosing period up to last dosing period. The washout period started 24 hours of last dose.

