7.7.2 Analysis of Categorical Pharmacodynamics Data

The following categorical PD parameters will be summarized by period (run-in [baseline], dosing periods [diary] or treatment period [questionnaire data], and washout) for each

appropriate population, using frequency distribution as specified in Section 7.1 (General Statistical Procedures).

Stool Diary PD parameters:

- Stage 1 CSBM based on dosing day diary
- Stage 1 SBM based on dosing day diary
- Success based on CSBM days per week (Stage 2 only) - primary efficacy outcome variable
 - The proportion of subjects for whom the drug was a success at the end of fixed period will be estimated with a binomial point estimate and corresponding 95% confidence interval. The observed proportion of successes will be compared to 0.10 using an exact binomial test. Success will be defined as an increase in CSBM/week of 1 or more OR a CSBM/week of 3 or more.

Sleep Diary PD parameters:

- Disappearance of arm or leg thrashing (Yes/no)

Questionnaire PD parameters:

- BDI-II Depression categories

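### In Stage 2, disappearance of arm or leg thrashing is more likely by chance in the 2-4 night dosing windows than in the 14-night run-in or washout, so its rates cannot be compared across periods.

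*SAP*

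**What the plan says.** SAP 4.4.2 introduces the sleep-diary outcomes with "the PD parameters for each period from sleep diary are as below". One of them is thrashing days per week, calculated as thrashing days divided by diary days, times seven. Disappearance is derived from it and "defined as zero days of arm or leg thrashing per week".

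For Stage 2, SAP 4.4 uses all run-in diaries and "all diaries in each dosing period up to last dosing period". SAP 7.7.2 lists "Disappearance of arm or leg thrashing (Yes/no" among the categorical outcomes to be summarised by run-in (baseline), dosing periods and washout. SAP 7.7 adds that PD variables are compared with baseline.

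The Stage 2 windows differ in length:

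- **Run-in:** 14 nights. Protocol 4.2 has the stool diary reviewed "at the end of the two week run-in period", and Protocol Appendix 7 has the sleep diary kept daily.
- **Escalation:** SAP 2.1 describes a "multiple dose escalation (3 dosing days at each dose" level. Protocol section 3 (Period 3.2) treats one level as a dosing period: "At the end of the second dosing period (100mg for 3 days".
- **Fixed dose:** in SAP 2.1, "subjects will continue to take this dose for 2-4 days". Protocol section 3 counts 5 to 7 consecutive days if the escalation days at that dose are included.
- **Washout:** two weeks (SAP 2.1).

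The SAP sets no common window length, no minimum number of diary nights and no restriction to patients who thrashed during run-in. Missing diaries are not imputed (SAP 8.3).

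**The concern.** Fourteen thrash-free nights imply that any three of them are thrash-free, but not the reverse. A yes/no outcome that requires no event in the window therefore favours short windows, whatever the drug does. Multiplying by seven puts the windows on a weekly scale but does not help, because zero stays zero.

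The Stage 2 table runs from a long window through short ones to a long one. With no drug effect it would tend to show few disappearances before dosing, more during dosing and fewer again after dosing stops. That is the shape a reader takes as evidence of a drug effect. There is little to correct that impression: the February 2018 amendment removed the randomised period, and SAP 7.7 plans no formal comparison with placebo. Missed diary entries shorten a window further and push the same way.

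**Working it through.** The documents state no figure for this outcome, so there is none to reproduce.

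**Inputs from the documents.** Windows of 14 nights (run-in, washout), 3 nights (one dose level), 2-4 nights (fixed dose) or 5-7 nights (fixed dose plus the escalation days at that dose).

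**Assumption.** The documents do not give the nightly probability of thrashing, p. It is varied below and held constant across periods, which means no drug effect.

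**Step 1: what the rule means.** (thrashing days / diary days) × 7 = 0 only if thrashing days = 0 in the whole window.

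**Step 2: independent nights.** P(no thrashing in k nights) = (1 − p)^k.

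| p | 3 nights | 14 nights |
|---|---|---|
| 0.05 | 0.95³ = 85.7% | 0.95¹⁴ = 48.8% |
| 1/7 (one night a week) | (6/7)³ = 63.0% | (6/7)¹⁴ = 11.5% (0.1155) |
| 0.30 | 0.70³ = 34.3% | 0.70¹⁴ = 0.7% |
| 0.50 | 0.50³ = 12.5% | 0.50¹⁴ = 0.006% |

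The difference is at least 10 percentage points for p from about 0.01 to 0.54. It is largest, 51.6 points, near p = 0.13, so p = 1/7 is close to the worst case in absolute terms.

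At p = 1/7 the fixed-dose window gives 73.5% for 2 nights and 54.0% for 4 nights. Counted as 5-7 nights it gives 46.3% to 34.0%. All exceed the 14-night figure. If 40 patients contributed to both columns, the expected counts would be 40 × 0.630 = 25.2 in a 3-night level and 40 × 0.1155 = 4.6 in the run-in.

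**Step 3: sensitivity at p = 1/7.**

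- **Patients differ** (beta-binomial, ICC ρ): P = B(a, b + k)/B(a, b), with a = p(1 − ρ)/ρ and b = (1 − p)(1 − ρ)/ρ. For ρ = 0.5, a = 1/7 and b = 6/7. Three nights give (6/7)/1 × (13/7)/2 × (20/7)/3 = 75.8%, and 14 nights give 61.8%. For ρ = 0.1 the pair is 66.0% and 26.8%; for ρ = 0.7 it is 80.0% and 72.7%.
- **Nights correlate** (first-order chain, lag-1 correlation c): P = (1 − p)(1 − p + cp)^(k−1). For c = 0.3 the pair is 69.4% and 21.8%; for c = 0.6 it is 76.2% and 39.9%.

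The gap shrinks but does not change direction.

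**Step 4: patients who never thrash.** With p = 0 they count as disappeared in every column, the run-in included. They raise all columns alike and dilute the gap rather than create it.

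**Step 5: what removes the bias.** With equal k the chance rates are equal, for example (6/7)⁴ = 54.0% in both windows. For days per week, the expected value is 7 × kp/k = 7p, whatever k is.

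**The case against.** **The 3-night columns are not certain.** SAP 7.7 provides summaries by dose level only if judged necessary. If escalation were shown as one period, Protocol section 3 allows up to 17 days, and that column would not be shorter than the run-in for a patient who escalates fully. This stands as a caveat. However, SAP 7.7.2 uses the plural dosing periods for diary data and keeps treatment period for questionnaires, and the fixed-dose window stays short on either reading.

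**Stage 1 differs.** For Stage 1 sleep diaries, SAP 4.4 adds the first 7 days after the last dosing period to that period and leaves only the second 7 days as washout. The last dosing window is then at least as long as washout, so the relapse pattern does not carry over. This stands, and the point is limited to Stage 2.

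**The stakes are modest.** SAP 4.4.2 calls the sleep diary exploratory, SAP 7.7.2 gives this outcome frequencies only, and SAP 7.7.1 already summarises thrashing days per week with its change from baseline. This too stands.

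**Stronger readings to avoid.** A reader might infer that the table will show false resolution and relapse. The documents give no nightly rate, and the gap is small when thrashing is very rare or nearly nightly, or when patients differ strongly, so it only could. A reader might also infer a spurious effect on REM sleep behaviour disorder, since Protocol 4.2 enriches for it. SAP 4.4.2 defines thrashing as fidgeting or leg twitching in the diary, and that disorder has its own questionnaire (SAP 4.4.3.8).

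**Conclusion.** The point holds for Stage 2. The rule as written makes the chance rate of disappearance depend on window length, and the SAP places unequal windows side by side. The direction follows from the definition and needs no assumption about the rate. The size does: at 3 versus 14 nights the gap is about 37 points at p = 0.05, 51 at 1/7, 34 at 0.30 and 12 at 0.50 with independent nights, and about 14 points at p = 1/7 with an ICC of 0.5. Labelling patients who never thrashed as having disappeared is a separate fault of definition that does not cause the gap. Because the outcome is exploratory and descriptive, the consequence is a table that could mislead. It deserves correction before database lock, but it does not touch the primary endpoint.

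**What to change.** For Stage 2, report disappearance only for the fixed-dose window. Compare it, patient by patient, with the same number of last run-in nights and the same number of washout nights. State which washout nights are used and the minimum number of diary nights required.

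Restrict the denominator to patients with at least one thrashing night in run-in week 1. The last 2-4 run-in nights, or the last 5-7 if the wider window is used, fall in week 2, so selection does not use the comparison nights. The chance rates are then equal as long as each patient's nightly rate is stable.

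Do not pool all on-treatment nights. Five levels of 3 nights plus 2-4 fixed-dose nights make 17-19. Under the amended 100-250 mg range, seven levels of 3 nights make 21 before any fixed dose. Both exceed the 14 run-in nights available for matching.

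Otherwise, drop the binary outcome and rely on thrashing days per week, whose mean does not depend on window length.

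The cost is SAP wording, one reprogrammed table and a smaller denominator. No new data are needed.

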4.4.3 Questionnaire Data

Questionnaire data will be considered as exploratory nature.

4.4.3.1 Non-Motor Symptoms Questionnaire

Non-Motor Symptoms Questionnaire (NMSQ) comprises 30-item questionnaire. The answer for each question is Yes/No (coded as 1/0). The total score will be calculated as a summed score over 30-items [1].

4.4.3.2 Beck Depression Inventory II

Beck depression inventory II (BDI-II) consists of 21 items. Each item is rated on a 4 point scale ranging from 0-3. For Question 16 and 18, the response categories are 0, 1a, 1b, 2a, 2b, 3a, or 3b. For the calculation of total score, the letters a and b will be dropped for these questions.

BDI-II total score will be calculated by summing the ratings for the 21 items based on the manual for Beck Depression Inventory-Second Edition. The maximum total score is 63.

Furthermore, total score will be classified into following categories.

BDI-II Total Scores	BDI-II Depression categories
0-13	Minimal
14-19	Mild
20-28	Moderate
29-63	Severe

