- 0 I don't feel that I look any worse than I used to.
- 1 I am worried that I am looking old or unattractive.
- 2 I feel there are permanent changes in my appearance that make me look unattractive
- 3 I believe that I look ugly.

15.

- 0 I can work about as well as before.
- 1 It takes an extra effort to get started at doing something.
- 2 I have to push myself very hard to do anything.
- 3 I can't do any work at all.

16.

- 0 I can sleep as well as usual.
- 1 I don't sleep as well as I used to.
- 2 I wake up 1-2 hours earlier than usual and find it hard to get back to sleep.
- 3 I wake up several hours earlier than I used to and cannot get back to sleep.

17.

- 0 I don't get more tired than usual.
- 1 I get tired more easily than I used to.
- 2 I get tired from doing almost anything.
- 3 I am too tired to do anything.

18.

0 My appetite is no worse than usual.

- 1 My appetite is not as good as it used to be.
- 2 My appetite is much worse now.
- 3 I have no appetite at all anymore.

19.

- 0 I haven't lost much weight, if any, lately.
- 1 I have lost more than five pounds.
- 2 I have lost more than ten pounds.
- 3 I have lost more than fifteen pounds.

20.

- 0 I am no more worried about my health than usual.
- 1 I am worried about physical problems like aches, pains, upset stomach, or constipation.
- 2 I am very worried about physical problems and it's hard to think of much else.
- 3 I am so worried about my physical problems that I cannot think of anything else.

21.

- 0 I have not noticed any recent change in my interest in sex.
- 1 I am less interested in sex than I used to be.
- 2 I have almost no interest in sex.
- 3 I have lost interest in sex completely.

INTERPRETING THE BECK DEPRESSION INVENTORY Now that you have completed the questionnaire, add up the score for each of the twenty-one questions by counting the number to the right of each question you marked. The highest possible total for the whole test would be sixty-three. This would mean you circled number three on all twenty-one questions. Since the lowest possible score for each question is zero, the lowest possible score for the test would be zero. This would mean you circles zero on each question. You can evaluate your depression according to the Table below. Total Score

Table below. Total Score	
Levels of Depression 1-10_	These ups and downs are considered normal
11-16	_ Mild mood disturbance
17-20	Borderline clinical depression

21-30	Moderate depression
31-40	Severe depression

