Informed Consent	X											
Inclusion/Exclusion Criteria	X											
Demographics/Medical History	X											
Prior and Con Meds	X											
Complete Physical Exam	X											X
Height	X											
Weight	X			X				X		X		X
Vital Signs ¹	X			X				X		X		X
ECG	X							X				X
Local Labs -Chemistry, Hematology	X							X		X		X
Local Labs - Urinalysis, Serum Pregnancy	X											
Fecal Occult Blood	X							X				X
Randomization								X				
Study Drug Dispense, Accountability, or Collection				X				X		X		
Reminder to Begin Taking Study Drug the Next Morning					X							
Instructions to Discontinue Laxatives and other BM Medication	X											
Instructions to Discontinue Laxatives and other BM medications												X
Stool and Sleep eDiary Instruction/Review	X	X	X	X	X	X	X	X	X	X	X	X
AE Review		X	X	X	X	X	X	X	X	X	X	X
Rome IV questionnaire	X		X									
UPDRS	X							X				X
PAC-QOL and PAC-SYM	X				X		X	X		X		X
Questionnaires- BDI, NMSQ, PFS-16, UM- PDHQ, MMSE, Trail-Making A and B, RBDQ and PDSS	X							X		X		X
Sitzmarks Capsule Distributions ²	X							X				
Reminder to Take Sitzmarks Capsules ³		X							X			
Abdominal X-Ray				X						X		
Dispense I-Button ⁴	X											

Scheduled Assessments	Period 3.1 Run-In					Period 3.2 Multiple Dose		Period 4 Randomized Treatment			Period 5 Wash-Out	
	Day 1 Visit 1	Days 2-7, 9- 10, 12-13 Calls	Day 8 Call	Day 11 Visit 2	Day 14 Call	Days. 1-13, 15-16 Calls	Day 14 Call	Day 1 Visit 3 ⁶	Days 2-5 Calls	Day 6 Visit 4	Days 1-7 Calls	Day 14 Visit 5
PK Draws & LFT ⁵								X		X		
Phone Call		X	X		X	X	X		X		X	

¹ For PK patients, vital signs taken pre-dose and 2 hours after dose. Blood pressure will be taken for all patients twice, first lying down and then after 5 minutes of sitting or standing from the recumbent position. All other vital signs will be measured after the patient has been resting in a sitting position for at least 5 minutes.

²Sitzmark capsules are dispensed to patients at Visit 1 with instructions to take one a day on Days 8, 9, and 10 of the Run-In period for the abdominal X-ray on Day 11. Patients will receive more Sitzmark capsules at Visit 3 with instructions to take one a day on Days 3, 4, and 5 of the Randomized Treatment period for the abdominal X-ray on Day 6.

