³Subjects are reminded during the Day 7 call of the Run-In period and Day 2 call of the Randomized Treatment period to begin taking the Sitzmark capsules the following day to prepare for the abdominal X-ray on Day 11 of the Run-In period and Day 6 of the Randomized Treatment period.

⁴Patients will wear an I-Button continuously from Day 8 of the Run-In period to Day 5 of the Wash-Out period except during periods of bathing.

⁵PK samples are taken pre-dose and 1, 2, 4, and 8 hours post-dose. A sample for liver function tests will be taken with the 8-hour post-dose PK draw.

⁶Visit 3 occurs on the day before randomization in non-PK subject

Table 4: Schedule of Events of Stage 2 under Protocol Dated 02 February 2018

Scheduled Assessments	Period 3.1 Run In					Period 3.2 Dose Escalation		Period 4 Fixed Dose		Period 5 Wash Out		
	Day 1 Visit 1 Screening	Days 2-7, 9,10,12,13 Phone Calls	Day 8 Phone Call	Day 11 Visit 2	Day 14 Phone Call	Days 1-13 Phone Calls	Day 14 Phone Call	Days 1-3 Phone Calls	Day 4 Visit 3	Days 1-7 Phone Calls	Day 14 Visit 4	Day 28 FU Call
Informed Consent	X											
Inclusion/Exclusion Criteria	X											
Demographics/Medical History	X											
Concomitant Medications	X	X	X	X	X	X	X	X	X	X	X	
Complete Physical Exam	X											X
Height	X											
Weight	X			X					X		X	
Vital Signs (1)	X			X					X		X	
EKG	X								X		X	
Local Labs: Chemistry*, Hematology*	X								X		X	
Local Labs: Coagulation Panel*	X											
Local Labs: Serum Pregnancy (2a) or FSH (2b)	X											
Urinalysis* (dipstick)	X								X		X	
Urine Pregnancy Test (3)				X					X		X	
Fecal Occult Blood (4)	X								X		X	
Study Drug Dispense, Accountability, Collection				X					X			
Reminder to Begin Taking Study Drug the Next					X							
Instruction to Discontinue Laxatives and Other Restricted Medications (5)	X											
Instruction to Resume Laxatives and Other Restricted Medications										X (6)		
Stool and Sleep Diary Instruction/Review	X	X	X	X	X	X	X	X	X	X	X	
AE Assessment and Review	X	X	X	X	X	X	X	X	X	X	X	X
Rome IV Questionnaire	X		X									
UPDRS	X								X		X	
PAC-QOL and PAC-SYM	X				X		X		X		X	
BDI-II, NMSQ, PFS-16, UM-PDHQ, MMSE, Trail-Making A and B, RBDQ, PDSS	X								X		X	
I-Button	X (7)		X						X (9)	X (10)		

* Refer to Appendix 1 for full list of clinical laboratory assessments

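### SAP 4.4.3.2 applies BDI-II response codes and severity bands to all patients in both stages, but the July 2017 protocol prints a BDI form with other options and bands, and no change of instrument is declared

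*SAP*

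**What the plan says.** **SAP 4.4.3.2** describes a single instrument: "Beck depression inventory II (BDI-II) consists of 21 items". On response codes it says "For Question 16 and 18, the response categories are 0, 1a, 1b, 2a, 2b, 3a, or 3b". On the total it says "BDI-II total score will be calculated by summing the ratings for the 21 items based on the manual for Beck Depression Inventory-Second Edition", and "The maximum total score is 63". The "total score will be classified into following categories": 0-13 minimal, 14-19 mild, 20-28 moderate, 29-63 severe. There is no rule for any other version of the scale.

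**Protocol (July 2017), Appendix 10** prints a form called simply BDI. Items 16 (sleep) and 18 (appetite) each have four unlettered options scored 0-3, worded only in terms of worse sleep and reduced appetite. The form has its own table of six bands: 1-10 normal, 11-16 mild mood disturbance, 17-20 ("Borderline clinical depression"), 21-30 moderate, 31-40 severe, over 40 extreme.

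**SAP schedules (section 2.1).** Table 2 (Stage 1) lists BDI. Table 3 (Stage 2, July 2017 protocol) reads "Questionnaires- BDI, NMSQ, PFS-16". Table 4 (Stage 2, February 2018 amendment) reads "BDI-II, NMSQ, PFS-16, UM-PDHQ, MMSE".

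**Use in the analysis.** SAP 4.4 applies the pharmacodynamic variables to both stages unless otherwise stated. SAP 7.7.1 summarises the BDI-II total and its change from baseline, and SAP 7.7.2 tabulates the BDI-II categories by period. SAP 7 analyses each stage separately. SAP 4.4.3 labels questionnaire data exploratory.

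**The concern.** The lettered response set in the SAP cannot be produced by the form printed in Appendix 10, so the difference is more than a label. The two band tables also cut the same 0-63 range at different points. Followed as written, the SAP would take totals from the Appendix 10 form and classify them with another instrument's cut-offs. That conflicts with SAP 8.3, under which questionnaire scores follow the instructions supplied with each form.

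What is at stake is the reading of one planned category table and of the total-score summaries beside it. A patient's depression category could depend on which table was applied, and a Stage 2 summary could combine scores from two forms without saying so. The SAP amendment was written partly to add scoring detail for each questionnaire (SAP 1), so this is the natural place to settle the matter.

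**Working it through.** **1. Reproduce the SAP's maximum.** 21 items × 3 points = 63. This agrees with SAP 4.4.3.2, and Appendix 10 states the same maximum. The range of the total is therefore common to both forms; the options on items 16 and 18 and the bands are not.

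**2. Classify every possible total (0 to 63, so 64 values) under both tables.**

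| Total | Appendix 10 band | SAP band |
|---|---|---|
| 0 | none (table starts at 1) | minimal |
| 1-10 | normal | minimal |
| 11-13 | mild mood disturbance | minimal |
| 14-16 | mild mood disturbance | mild |
| 17-19 | borderline | mild |
| 20 | borderline | moderate |
| 21-28 | moderate | moderate |
| 29-30 | moderate | severe |
| 31-40 | severe | severe |
| 41-63 | extreme | severe |

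**3. Count the totals whose severity differs.** Normal (and a total of 0) is matched to minimal, and extreme to severe. The borderline band has no SAP counterpart, so it has to be placed on one side or the other.

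- Borderline grouped with mild: 11-13 (3 totals), 20 (1) and 29-30 (2) differ. 3 + 1 + 2 = 6 of 64.
- Borderline grouped with moderate: 11-13 (3), 17-19 (3) and 29-30 (2) differ. 3 + 3 + 2 = 8 of 64.

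Totals 17-19 and the total of 20 cannot both count as severity shifts, because each arises only under the opposite placement. The direction is mixed: 11-13 (and 17-19) move to a lower category under the SAP, while 29-30 (and 20) move to a higher one. The extreme band, 41-63, is absorbed into severe; that loses a distinction but is not counted as a severity shift here.

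**4. Where forms could be combined.** Because stages are summarised separately, Stage 1 involves only the form scheduled in SAP Table 2: if that was the Appendix 10 form, Stage 1 is mis-banded but not mixed. Stage 2 includes patients under both protocol versions, and neither SAP 7.7.1 nor 7.7.2 splits these scores by version. Mixing is possible only there.

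**5. Is a change of instrument declared?** SAP 2.1 describes the amendment as altering the Stage 2 dose range and removing randomization, and says nothing else changed. SAP 5.1 reports no changes from the protocol's planned analyses. SAP 9 lists only two dropped secondary analyses. None mentions the depression scale.

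**The case against.** The strongest reply is that nobody can tell from these documents which form patients completed, and BDI-II may have been in use from the start. SAP 2.1 says the amendment changed nothing beyond dose range and randomization; taken literally, BDI in Tables 2-3 and BDI-II in Table 4 would name one instrument. Naming is loose elsewhere: the SAP's abbreviation list has only BDI although its text uses BDI-II, and the protocol says UPDRS but prints the MDS version. The protocol's appendices are not a reliable guide to the SAP's instruments either. PAC-QOL in Appendix 17 mixes 1-5 and 0-4 codes where the SAP uses 0-4 throughout. The lettered codes in SAP 4.4.3.2 may reflect data actually collected. SAP 8.3 also allows special handling to be documented in the dataset specifications.

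Most of this stands, and it makes the consequence conditional. It does not remove the conflict. The no-other-changes sentence is not fully reliable, since Table 4 also shows items absent from Table 3, such as a Day 28 follow-up call. SAP 8.3 gives a route to form-specific scoring but does not override the specific bands in 4.4.3.2; on the Appendix 10 form the two instructions contradict each other.

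Two stronger readings are tempting. A reader might infer that the tables will certainly misclassify and pool two instruments; the documents do not establish that two forms were used. A reader might also infer that all 10 Stage 1 patients and every July 2017 Stage 2 patient would be wrongly classified. All of them would be exposed to the wrong bands if the scheduled form was used, but only totals in the discordant ranges change category.

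**Conclusion.** The documents conflict, and the SAP as written has no valid rule for the form that the July 2017 protocol prints. If that form was used as scheduled, severity is misassigned for 6 or 8 of the 64 possible totals, depending on where the borderline band is placed. These are shares of the score range, not of patients: no score distribution is given, nor the number of Stage 2 patients under each protocol version, so the number affected cannot be computed. The use of BDI-II after the amendment rests on SAP Table 4, because the February 2018 protocol text is not among the documents. If BDI-II was used throughout, the category tables are right, and the error lies in Appendix 10 and in the labels of SAP Tables 2 and 3.

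The point is minor. The categories receive a frequency table by period with no test or decision attached, the data are exploratory, and the primary endpoint, its test and the sample size are unaffected.

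**What to change.** Confirm which depression form was completed under each protocol version, and record it for each patient.

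- **If the forms differ:** band each form by its own table, or limit the BDI-II category table to patients who completed BDI-II. Show Stage 2 totals and change from baseline by form. Declare the change of instrument in SAP 5.1 and SAP 9.
- **If BDI-II was used throughout:** correct Appendix 10 and the BDI labels in SAP Tables 2 and 3; the scoring in SAP 4.4.3.2 can stay.

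The cost is a few sentences in the SAP and, in the first case only, a split by form in the exploratory depression summaries, with smaller cells as the downside.
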